2 INTRODUCTION

This statistical analysis plan (SAP) addresses the planned analyses for the clinical study entitled “Post-Market Real World Outcomes in WATCHMAN FLX™ Pro Left Atrial Appendage Closure (LAAC) Device” (HEAL-LAA), based on the approved protocol version B. Approximately 1000 consented subjects will be enrolled. Data for subjects receiving the WATCHMAN FLX Pro device will be collected over 12 months.

3 ENDPOINT ANALYSIS

Four planned subset analyses will be conducted:

- Primary analysis subset: Initial 500 enrolled subjects
- Access system subset
- Diversity subset
- Full enrollment set (all enrolled subjects)

3.1 Primary Efficacy Endpoint

The following hypothesis tests are only based on the primary analysis subset.

3.1.1 Hypotheses

The objective of the primary efficacy endpoint analysis is to test the null hypothesis that the rate of leak >5 mm at 45-day post-implant core-lab TEE for the WATCHMAN FLX Pro primary analysis subset is greater than or equal to 5%. A one-sample z-test will be used to test the one-sided hypothesis.

$$H_0: P_{WM_Leak} \geq 5\%$$

$$H_1: P_{WM_Leak} < 5\%$$

3.1.2 Sample Size

The sample size was estimated based on the following assumptions:

- Expected rate for WATCHMAN FLX Pro $< 2\%$ (based on historic studies of FLXibility and PINNACLE FLX)
- Testing margin = 3%
- PG = 5% = expected rate (2%) + testing margin (3%)
- 1-sided significance level (α) = 0.025
- Power (1 minus β) $> 85\%$

- Number of evaluable subjects = 400
- Expected attrition rate = 20%

Given the above assumptions, 500 subjects of primary analysis subset will be required.

3.1.3 Statistical Methods

The primary analysis subset with a completed 45-day follow-up TEE will be eligible for inclusion in this endpoint analysis. The primary analysis subset with core lab-completed 45-day TEE will be included in the denominator for the primary effectiveness event rate. The primary analysis subset with core lab-completed 45-day TEE and demonstrated leak $>5\text{mm}$ will be included in the numerator. A one-sample z-test will be used to test the assumption that the rate of leak $>5\text{ mm}$ at 45-day post-implant TEE is $\geq 5\%$. The null hypothesis will be rejected if the resulting p-value is less than 0.025.

3.2 Primary Safety Endpoint

The primary safety endpoint is the composite rate of CEC-adjudicated all-cause mortality, all stroke, systemic embolism, and major bleeding at 6 months. The following hypothesis tests are based on the primary analysis subset.

3.2.1 Hypotheses

The objective of the primary safety endpoint analysis is to test the null hypothesis that the composite rate of CEC-adjudicated all-cause mortality, all stroke, systemic embolism, and major bleeding at 6 months for the WATCHMAN FLX Pro primary analysis subset is greater than or equal to the performance goal (PG; 21%). A one-sample Z-test will be used to test the one-sided hypothesis.

$$H_0: P_{\text{safety}} \geq 21\%$$

$$H_1: P_{\text{safety}} < 21\%$$

3.2.2 Statistical Methods

The primary analysis subset with sufficient 6-month follow-up will be eligible for inclusion in this endpoint analysis. The primary analysis subset with sufficient 6-month follow-up will be included in the denominator for the primary safety event rate. Subjects in the primary analysis subset with the occurrence of one of the following events between the time of implant and 6-month following the procedure will be included in the numerator for the primary safety event rate: all-cause mortality, all stroke, systemic embolism, and major bleeding.

A one-sample Z-test will be used to test the assumption that the composite rate of all-cause mortality, all stroke, systemic embolism, and major bleeding at 6 months $\geq 21\%$. The null hypothesis will be rejected if the resulting p-value is less than 0.025.

3.3 Primary Endpoint for Access System Subset

The primary endpoint for access system subset is the implant success rate, which is defined as implantation of a WATCHMAN FLX Pro device in the correct anatomical

position using the WATCHMAN TruSteer Access System. The implanted success rate will be evaluated by number of TruSteer Implant/number of subjects in the access system subset *100%. The analysis subsets are defined in 4.1.

The following hypothesis tests are based on the access system subset.

3.3.1 Hypotheses

A one-sample z-test will be used to test the null hypothesis that the implant success rate is less than PG:

$$H_0: P_{\text{TruSteer}} \leq 94\%$$

$$H_1: P_{\text{TruSteer}} > 94\%$$

3.3.2 Sample Size

The sample size was estimated based on the following assumptions:

- Expected rate for implant success in the access system subset $\geq 97.8\%$ (based on historic studies of FLXibility, ICE LAA, WATCHMAN FLX-SURPASS, WATCHMAN FLX HK and PINNACLE FLX)
- Testing margin = 3.8%
- PG = 94% = expected rate (97.8%) - testing margin (3.8%)
- 1-sided significance level (α) = 0.025
- Power (1 minus β) $> 90\%$

Given the above assumptions, 300 subjects of access system subset will be required.

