11.3.4. Subset Analyses

The following subset will be analyzed for the Primary Endpoints and the Additional Endpoints within the study:

- Primary Analysis Subset

The Primary Analysis Subset consists of data from the initial 500 enrolled subjects.

Note: The hypothesis tests (PGs) are only based on the Primary Analysis Subset.

The following subsets will be analyzed per the Statistical Analysis Plan:

- Access System Subset
- Diversity Subset
- Full Enrollment Set (all enrolled subjects)

Note: All subset analysis as outlined within the Statistical Analysis Plan will be reported within the final clinical study report.

Subjects may meet more than one subset requirement and therefore may have their data analyzed in multiple subsets. Requirements for each subset will be outlined in the Enrollment Guide.

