3.3.3 Statistical Methods

All enrolled subjects in the access system subset will be eligible for inclusion in this endpoint analysis. All enrolled subjects in the access system subset will be included in the denominator and access system subset with implant success will be included in the numerator.

A one-sample z-test will be used to test the null hypothesis that the implant success rate $\leq 94\%$. The null hypothesis will be rejected if the resulting p-value is less than 0.025.

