4.2 Analysis Sets

Endpoints will be analyzed on an intention-to-treat (ITT) basis and an implanted basis. For ITT analyses, all subjects who sign the IEC-approved study ICF and are enrolled in the study will be included in the analysis, whether or not a study device was implanted. For implanted analyses, ITT subjects who had the study device implanted in the correct position during the index procedure will be included in the analysis.

- Primary analysis subset

The initial 500 patients enrolled in HEAL-LAA will be included in the primary analysis subset. Primary endpoints will be assessed on an intention-to-treat (ITT) basis and an implanted basis. The ITT analysis set includes all subjects who sign an Informed Consent Form, meet all clinical inclusion and no clinical exclusion criteria, and the WATCHMAN FLX Pro device has been used for treatment and/or attempted to be used for treatment. The hypothesis tests (PGs) are only based on the Primary Analysis Subset.

- Access system subset

The initial 300 TruSteer Attempt or TruSteer Implant subjects will be included in access system subset.

- Diversity Subset

Non-Caucasian subjects will be included in the diversity subset. There is no formal statistical hypothesis for this subset.

- Full enrollment set

All enrolled subjects will be included in this subset. There is no formal statistical hypothesis for this subset.

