4.4 Number of Subjects per Investigative Site

To avoid any site effect and bias, no site will be authorized to implant or attempt more than 15% of the primary analysis subset (first 500 enrolled subjects) ($n = 75$) without prior approval from the sponsor. Subjects exceeding this enrollment cap will be excluded from primary analysis set, but will still be retained in the full enrollment set. Sites that have reached the general enrollment cap may enroll additional subjects within the Diversity Subset. Enrollment cap waivers may be given for access system subset enrollment per the enrollment guide. To avoid any site effect and bias, no site will be authorized to implant or attempt more than 20% of the access system subset subjects ($n = 60$) without prior approval from the sponsor. Subjects exceeding this enrollment cap will be excluded from access analysis set, but will still be retained in the full enrollment set.

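### The Access System z-test names no variance: at 10 or 11 failures in 300 the choice decides the verdict, and the version behind the sample size has 87.1% exact power at 97.8%, not above 90%

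*SAP*

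**What the plan says.** The Access System Subset has its own formal endpoint in SAP 3.3: the proportion of subset subjects implanted in the correct position using the TruSteer system. SAP 3.3 introduces the test with "The following hypothesis tests are based on the access system subset". SAP 3.3.1 sets H0 as a rate of at most 94% and describes the test as follows: "A one-sample z-test will be used to test the null hypothesis that the implant success rate is less than PG". SAP 3.3.3 puts every enrolled subset subject in the denominator and adds: "The null hypothesis will be rejected if the resulting p-value is less than 0.025". None of these sections gives a standard error, a continuity correction, a cut-off count or a confidence-bound rule.

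SAP 3.3.2 lists an expected rate of at least 97.8%, a margin of 3.8 points, one-sided alpha of 0.025 and power above 90%, and concludes: "Given the above assumptions, 300 subjects of access system subset will be required". SAP 4.2 fixes membership: "The initial 300 TruSteer Attempt or TruSteer Implant subjects will be included in access system subset". The site-cap paragraph (the second of two SAP sections numbered 4.4) can reduce that number: "Subjects exceeding this enrollment cap will be excluded from access analysis set".

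On the standing of the test, the Primary Analysis Subset bullet of SAP 4.2 says "The hypothesis tests (PGs) are only based on the Primary Analysis Subset", and Protocol 11.3.4 carries the same note. The protocol contains no Access System test and leaves that subset's analysis to the SAP.

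**The concern.** A formal success criterion should give one verdict for every possible count. Here two standard forms of the one-sample z-test both fit the wording. Near a 94% goal they differ materially, because the observed-rate variance shrinks as the observed rate rises above the goal. If the choice is made after the count is known, a pass at 10 or 11 failures can be challenged as a choice driven by the result.

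The second issue is whether the stated power and the stated alpha can both be had at the SAP's own planning rate. With about 6.6 failures expected in 300 (300 × 0.022), the rejection region moves in whole failures, and a normal approximation can misstate the power.

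A smaller point concerns the wording that confines performance-goal tests to the Primary Analysis Subset. Read literally, it excludes the test that SAP 3.3 sets up. The intersection-union argument in SAP 4.4 (Control of Type-I Error) also covers only the Primary Analysis Subset.

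**Working it through.** **Inputs (SAP 3.3.1 to 3.3.3).** p0 = 0.94, p1 = 0.978, difference 0.038, one-sided alpha 0.025 (z = 1.96), target power 90% (z = 1.2816), n = 300. A failure is any subset subject who is not a TruSteer Implant.

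**Step 1: reproduce the plan's figure.** With the null variance in the test:

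- N = [(1.96·√(0.94·0.06) + 1.2816·√(0.978·0.022)) / 0.038]² = 295.7, so 296.
- Approximate power at 300 = Φ[(0.038 − 1.96·√(0.0564/300)) / √(0.021516/300)] = Φ(1.314) = 0.9055.

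Both agree with 300 subjects and power above 90%. With the p1 variance throughout, as an observed-rate test would be planned, N = (1.96 + 1.2816)²·0.021516/0.038² = 156.6, so 157. The sample size therefore points to the null variance.

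**Step 2: the verdict by count at n = 300.** Null-variance z = (p̂ − 0.94)/√(0.0564/300). Observed-rate z = (p̂ − 0.94)/√(p̂(1 − p̂)/300). Exact p = P(F ≤ f), where F is Binomial(300, 0.06).

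| Failures | p̂ | p, null variance | p, observed rate | p, exact |
|---|---|---|---|---|
| 9 | 97.00% | 0.0143 pass | 0.0012 pass | 0.0132 pass |
| 10 | 96.67% | 0.0259 fail | 0.0050 pass | 0.0268 fail |
| 11 | 96.33% | 0.0444 fail | 0.0158 pass | 0.0497 fail |
| 12 | 96.00% | 0.0723 fail | 0.0385 fail | 0.0850 fail |

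The one-sided 97.5% lower bound at 10 failures shows the same split: 93.96% by Clopper-Pearson, and 96.67% − 1.96·√(0.9667·0.0333/300) = 94.64% by the observed-rate formula.

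**Step 3: exact operating characteristics at n = 300.**

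| Test | Failures allowed | True alpha at 94% | Power at 97.8% | Power at 98.0% |
|---|---|---|---|---|
| Null-variance z, or exact binomial | 9 | 1.3% | 87.1% | 91.8% |
| Observed-rate z | 11 | 5.0% | 96.4% | 98.1% |

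The 9-failure rule reaches 90% power only at a true rate of about 97.92%. At 97.8% the risk of missing the goal is 100 − 87.1 = 12.9%, against the 10% implied by the SAP.

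**Step 4: how often the two z-tests disagree.** P(10 or 11 failures) is 9.3% at a true rate of 97.8%, 6.3% at 98.0% and 3.7% at 94%. This is the chance of conflicting verdicts, not of a wrong decision.

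**Step 5: dependence on the final n.** The exact cut-off is 8 failures at n = 280, 9 for n = 281 to 302, and 10 at n = 303. The null-variance z-test agrees with it from 281 to 301. At n = 280 and n = 302 it allows one more failure, with true alpha 2.55% and 2.52%.

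**The case against.** The strongest reply is that the SAP's arithmetic is not wrong. Its 300 subjects and power above 90% follow from the usual normal approximation, 97.8% is written as a floor, and 90% exact power is reached only 0.12 points above it. Ten failures miss 0.025 by just 0.0009 under the null variance. All of that is correct, and the gap is a discreteness effect. But a power claim has to hold at the floor it is quoted for, and there the exact figure is 87.1%.

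The ambiguity can also be called narrow. The design fits the null variance, and unlike the two primary endpoints this one has no confidence-bound sentence that might suggest an observed-rate interval. That supports the null-variance reading, but nothing in the analysis text rules out the other one.

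It is also fair to say that a clause placing the standard error under the 94% goal would settle every disputed count while keeping the z-test. The exact test is preferable because it holds alpha at every n, and at n = 300 it costs nothing. Cap exclusions can only lower n from 300, and the exact cut-off stays at 9 down to 281.

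The point about exclusive wording is editorial. In SAP 4.2 the sentence sits inside the Primary Analysis Subset bullet, and a formal hypothesis is denied only to the Diversity and Full Enrollment sets. SAP 4.4 already sets one-sided 2.5% for all study endpoints.

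**Conclusion.** The concern holds. SAP 3.3 leaves the variance open, and at n = 300 that decides the result at exactly 10 and 11 failures. Neither z-test gives both properties the SAP claims at 97.8%: the null-variance test controls alpha (1.3%) but has 87.1% exact power, while the observed-rate test exceeds 90% power (96.4%) at a true alpha of 5.0% against the stated 2.5%.

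These figures assume 300 analysed subjects, independent outcomes with a common success rate, and no continuity correction. The design itself is sound and the power shortfall is 2.9 points, so this should be corrected but does not call for redesign.

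**What to change.** - **SAP 3.3.1 and 3.3.3:** name the exact binomial test at one-sided 0.025. Give 9 or fewer failures in 300 as an illustration, and state that the cut-off is recomputed from the final subset size.
- **SAP 3.3.2:** restate attained power at n = 300 as about 87% at 97.8% and about 92% at 98.0%.
- **SAP 4.2 and Protocol 11.3.4:** reword the exclusive statement so that it refers to the leak and 6-month safety goals.
- **SAP 4.4 (Control of Type-I Error):** state that the Access System goal is tested separately at its own one-sided 2.5%, outside the intersection-union argument.

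The cost is a few sentences in the SAP, one protocol note and a slightly less favourable stated power. No additional subjects are needed, and no power is lost against the test that the sample size supports, because the two cut-offs are the same at n = 300. The SAP changes can be made as an amendment approved before the analysis, as SAP 5.6 provides.

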3.3.3 Statistical Methods

All enrolled subjects in the access system subset will be eligible for inclusion in this endpoint analysis. All enrolled subjects in the access system subset will be included in the denominator and access system subset with implant success will be included in the numerator.

A one-sample z-test will be used to test the null hypothesis that the implant success rate $\leq 94\%$. The null hypothesis will be rejected if the resulting p-value is less than 0.025.

4 GENERAL STATISTICAL METHODS

4.1 Subject Status and Classification

4.1.1 Screen Failure

A subject who signs an ICF but does not meet clinical eligibility criteria and/or is not treated or attempted to be treated with a WATCHMAN FLX Pro device is considered a screen failure. These subjects do not count towards the enrollment ceiling and will not be used for any planned endpoint analyses.

4.1.2 Attempt

A subject who signs an ICF, meets eligibility criteria, and has had a WATCHMAN Access Sheath inserted to implant the device, but does not receive a WATCHMAN FLX Pro device will be classified as “Attempt.” Attempt subjects will be used for analyses of the ITT analyzed endpoints.

4.1.3 Implant

A subject who signs an ICF, meets eligibility criteria, and is implanted with the WATCHMAN FLX Pro device will be classified as “Implant.” These subjects are followed in accordance with the follow-up schedule and included in all study analyses.

4.1.4 TruSteer Attempt

A subject who attempted with WATCHMAN TruSteer Access System but does not receive a WATCHMAN FLX Pro device with WATCHMAN TruSteer Access System will be classified as “TruSteer Attempt”. Subjects who attempted with WATCHMAN TruSteer Access System but receives the device with other Access System will be also classified as “TruSteer Attempt”. These subjects will be included in Access System Subset analyses.

4.1.5 TruSteer Implant

A subject who receives a WATCHMAN FLX Pro device with WATCHMAN TruSteer Access System will be classified as “TruSteer Implant”. These subjects will be included in Access System Subset analyses.

4.2 Analysis Sets

Endpoints will be analyzed on an intention-to-treat (ITT) basis and an implanted basis. For ITT analyses, all subjects who sign the IEC-approved study ICF and are enrolled in the study will be included in the analysis, whether or not a study device was implanted. For implanted analyses, ITT subjects who had the study device implanted in the correct position during the index procedure will be included in the analysis.

- Primary analysis subset

The initial 500 patients enrolled in HEAL-LAA will be included in the primary analysis subset. Primary endpoints will be assessed on an intention-to-treat (ITT) basis and an implanted basis. The ITT analysis set includes all subjects who sign an Informed Consent Form, meet all clinical inclusion and no clinical exclusion criteria, and the WATCHMAN FLX Pro device has been used for treatment and/or attempted to be used for treatment. The hypothesis tests (PGs) are only based on the Primary Analysis Subset.

- Access system subset

The initial 300 TruSteer Attempt or TruSteer Implant subjects will be included in access system subset.

- Diversity Subset

Non-Caucasian subjects will be included in the diversity subset. There is no formal statistical hypothesis for this subset.

- Full enrollment set

All enrolled subjects will be included in this subset. There is no formal statistical hypothesis for this subset.

4.3 Control of Systematic Error/Bias

To control for the potential bias that could be introduced via sponsor classification of adverse events, an independent core laboratory will be used for analysis of certain endpoints at prespecified time points. A Clinical Events Committee (CEC) will adjudicate key endpoints and relevant adverse events.

4.4 Control of Type-I Error

For the primary analysis subset, due to the requirement that each applicable endpoint must be passed, each applicable endpoint can be tested at the significance level of 5% while still maintaining the overall type-I error level at no greater than 5%. This follows the methodology of the Intersection-Union Test (IUT). All study endpoints will be analyzed using one-sided significance levels of 2.5%.

4.4 Number of Subjects per Investigative Site

To avoid any site effect and bias, no site will be authorized to implant or attempt more than 15% of the primary analysis subset (first 500 enrolled subjects) ($n = 75$) without prior approval from the sponsor. Subjects exceeding this enrollment cap will be excluded from primary analysis set, but will still be retained in the full enrollment set. Sites that have reached the general enrollment cap may enroll additional subjects within the Diversity Subset. Enrollment cap waivers may be given for access system subset enrollment per the enrollment guide. To avoid any site effect and bias, no site will be authorized to implant or attempt more than 20% of the access system subset subjects ($n = 60$) without prior approval from the sponsor. Subjects exceeding this enrollment cap will be excluded from access analysis set, but will still be retained in the full enrollment set.

5 ADDITIONAL DATA ANALYSES

The additional data analysis in this section will be applied to all four analysis subsets: primary analysis subset, access system subset, diversity subset, and full enrollment set.

5.1 Other Endpoints/Measurements

No statistical hypothesis test will be conducted for other endpoints/measurements. The variables of interest will be summarized using descriptive statistics for continuous variables (e.g., mean, standard deviation, n, minimum, maximum) and frequency tables or proportions for discrete variables. The Kaplan-Meier product-limit method will be used to estimate rates for time-to-event endpoints. Adverse event and serious adverse event (SAE) rates will be reported.

Additional endpoints will include the following:

1. CEC-adjudicated:

- Device Success: Defined as implantation of a WATCHMAN FLX Pro device without in-hospital mortality.
- All-cause mortality: Cardiovascular/unknown death and non-cardiovascular death
- All Stroke: Disabling and non-disabling stroke; ischemic and hemorrhagic stroke
- Bleeding: International Society on Thrombosis and Haemostasis (ISTH) major and non-major clinically significant
 - Procedural bleeding and non-procedural bleeding
- Pericardial effusion/tamponade requiring pericardiocentesis or surgery
- Systemic embolism

2. Site reported:

- Device-related thrombus

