7.2 Methods for Handling Missing Data

All subjects who are enrolled will be eligible for evaluation, regardless of the treatment that ensues. Handling of dropouts and missing data will depend on their frequency and the nature of the outcome measure. Adjustments for missing outcomes data will be performed if deemed necessary to eliminate or minimize bias and will be described completely. Statistical models that account for censored data will be employed in appropriate circumstances, e.g., for time-to-event outcomes. Outlier values will be evaluated, and values determined to be invalid will be queried. All data will be included in the analysis unless judged to be invalid.

When calculating rates of adverse events for specific time intervals, missing and partial dates will be handled as shown below:

Partial Date Description	Action Taken
Entire onset date is missing	The implant procedure date will be used for

	the onset date.
The month and the day of the month are missing but the year is available	January 1 st will be used for the month and day of the onset date. However, if the imputed date falls before the implant procedure date, then the implant procedure date will be used for the onset date.
Day is missing, but the month and year are available	The 1 st will be used as the day of the onset date. However, if the imputed date falls before the implant procedure date, then the implant procedure date will be used for the onset date.

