7.3 Rules and Definitions

Binary event rates (proportions) will be calculated on a per subject basis.

The number of subjects included in the safety endpoint outcome rates will be based on subjects who have adequate follow-up (see Section **Error! Reference source not found.**) and/or have experienced any CEC-confirmed events.

For baseline categorical variables, “unknown” responses and missing values will not be counted in rate denominators.

The date of last follow-up will be the latest of the following dates for each subject: site-reported adverse event date, CEC-confirmed event date, index procedure date, discharge date, follow-up visit date, and patient withdrawal (defined as: reasons = xx, xx, xx reasons) date from the end of study form.

Days to (event or last known status) = (event or status) date minus procedure date.

Note: subject withdrawal date should always be the last follow-up date and death date should be the subject last follow-up date if the subject didn't withdraw prior to death.

Length of hospital stay = discharge date minus procedure date.

In-hospital event rates are calculated as the proportion of subjects who experience the specified event from index procedure through day of discharge out of all subjects enrolled.

Out-of-hospital event rates are calculated as the proportion of subjects who experience the specified event from the day after discharge through the number of days as specified out of all subjects who were discharged following index procedure and have adequate follow-up or have experienced the event as specified.

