7.4 CEC Binary Event Rates

The calculation method will follow the table below and extend to other endpoints and time points (e.g., 1-year death) with the appropriate modifications to the numbers of days. For example, for 90 days the event must have occurred within 90 days of procedure and the valid data point must be 60 days (early portion of window for the 90-day visit).

The following are the maximum days to event and number of days post-procedure that are adequate follow-up:

Follow-up Visit	Maximum Days to Event*	Days for Adequate Follow-up**
45 Days	45	30
6 Months	180	150
1 Year	365	335

*this is the target date for the follow-up visit except for the 1-year visit where this is the end of the visit window

**this is the start of the visit window

All event rates will be calculated relative to the date of index procedure (i.e., post-procedure).

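### Where Kaplan-Meier is used for stroke, embolism, bleeding, effusion or cause-specific death, it censors deaths and slightly overstates the rate; the SAP does not say which method supplies the reported rates

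*SAP*

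**What the plan says.** SAP 5.1 covers the additional endpoints. It says that "The Kaplan-Meier product-limit method will be used to estimate rates for time-to-event endpoints", and also that "No statistical hypothesis test will be conducted for other endpoints/measurements". The list that follows includes "All Stroke: Disabling and non-disabling stroke; ischemic and hemorrhagic stroke" and "Bleeding: International Society on Thrombosis and Haemostasis (ISTH) major and non-major clinically significant", together with systemic embolism, pericardial effusion or tamponade needing intervention, and death split into cardiovascular/unknown and non-cardiovascular. The opening of SAP section 5 applies all of this to each of the four analysis subsets.

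On follow-up time, SAP 7.3 says that "death date should be the subject last follow-up date", provided the subject had not withdrawn first. The only general rule on censoring is in SAP 7.2: "Statistical models that account for censored data will be employed in appropriate circumstances, e.g., for time-to-event outcomes". Neither document names a cumulative incidence or competing-risk method.

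The SAP also contains a second estimator. Under SAP 7.3, "Binary event rates (proportions) will be calculated on a per subject basis", and the denominator for the safety rates takes in subjects with enough follow-up and/or any CEC-confirmed event. SAP 7.4 gives the day limits for 45 days, 6 months and 1 year and extends the method to other endpoints and time points. Nothing in 5.1, 7.3 or 7.4 says which estimator produces the reported rate for a given component.

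**The concern.** A patient who dies without a stroke can no longer have one. Kaplan-Meier for stroke treats that patient as censored, that is, as still at the same risk as those who remain under observation. One minus Kaplan-Meier then estimates the stroke rate that would apply if nobody died, which is never below the proportion of patients who actually have a stroke. The same holds for embolism, bleeding and effusion. It also holds for cardiovascular death, where non-cardiovascular death is the competing event, and the reverse.

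Two things are at stake. The component rates are a main product of the study: Protocol 6.1 makes collection of real-world outcomes the primary objective, and Protocol 7.3 expects the data to support regulatory submissions. In addition, with two estimators in the SAP and no rule for choosing between them, two different rates for the same component could both comply with the plan.

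**Working it through.** **1. The plan's own figures.** No stated design figure depends on Kaplan-Meier. The nearest is the power for the primary safety endpoint (SAP section 1: 14% expected, performance goal 21%, one-sided 0.025, 485 evaluable):

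- Power = Φ[(0.07 − 1.96 × √(0.21 × 0.79/485)) / √(0.14 × 0.86/485)] = Φ[(0.0700 − 0.0362)/0.0158] = 98.4%, which meets the stated figure of above 95%.
- 485/(1 − 0.03) = 500, as stated.

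The same formula for the leak endpoint (400 evaluable, 2% against 5%) gives 89.1%, which meets the stated figure of above 85%, and 400/0.8 = 500. Both primary endpoints are binary proportions, and the safety composite counts death as an event, so neither figure changes below.

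**2. Inputs for the size of the bias.** The documents give no mortality rate, so cumulative mortality D is assumed at 2%, 5%, 10% and 15%. The component rates K shown by one minus Kaplan-Meier (3%, 8%, 10%) are also illustrative. Hazards are taken as constant.

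**3. Formula.** With λk = −ln(1 − K) and λd = −ln(1 − D), the cumulative incidence with death as competing event is

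CIF = λk/(λk + λd) × [1 − (1 − K)(1 − D)].

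Example, K = 8% and D = 5%: λk = 0.0834, λd = 0.0513, so CIF = 0.619 × (1 − 0.92 × 0.95) = 0.619 × 0.126 = 7.80%. The overstatement is 0.20 points, or 2.6% relative.

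| Assumed mortality | CIF when KM shows 3% | CIF when KM shows 8% | CIF when KM shows 10% | Relative overstatement |
|---|---|---|---|---|
| 2% | 2.97% | 7.92% | 9.90% | about 1.0% |
| 5% | 2.92% | 7.80% | 9.75% | about 2.6% |
| 10% | 2.85% | 7.60% | 9.50% | about 5.3% |
| 15% | 2.77% | 7.39% | 9.24% | about 8.3% |

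The relative overstatement is roughly D/2. In absolute terms it runs from 0.03 points (3% component, 2% mortality) to 0.76 points (10% component, 15% mortality).

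**4. Anchoring to the plan.** The one relevant rate in the documents is the expected 6-month composite of below 14%. Hold it at 14% and split it between death and non-fatal events. With an even split the non-fatal cumulative incidence is 7.00%, and one minus Kaplan-Meier is 1 − √0.86 = 7.26%, an excess of 0.26 points. For non-fatal shares from 20% to 80% the excess lies between 0.17 and 0.26 points.

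**5. If hazards are not constant.** Were every death to precede every component event, the relative overstatement would reach 1/(1 − D) − 1: 5.3% at D = 5% and 11.1% at D = 10%.

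**6. Additivity of cause-specific death.** Suppose Kaplan-Meier gives 5% for each cause and the causes are independent. All-cause mortality is then 1 − 0.95 × 0.95 = 9.75%, while the two reported components sum to 10%.

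**The case against.** The strongest reply is that SAP 5.1 never assigns Kaplan-Meier to stroke or bleeding by name. It speaks of time-to-event endpoints in general, beside frequency tables and proportions for discrete variables. The binary method in 7.3 and 7.4 is built for CEC events, and all-cause mortality is itself CEC-adjudicated. A patient who dies without a stroke therefore stays in the stroke denominator as a non-event, and that rate is free of the bias. It may well be the intended source of the component rates. This stands, and it is why the point is conditional on Kaplan-Meier being used. It does not remove the point: the 5.1 sentence carries no exception, most of the listed endpoints are dated clinical events, and the SAP does not choose between the methods.

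The effect is also small beside sampling error. For a 10% rate the 95% half-width is 1.96 × √(0.1 × 0.9/500) = 2.6 points at 500 subjects and 1.9 points at 1000, against 0.25 points of bias at 5% mortality and 0.50 at 10%. This stands too, although bias does not shrink as subjects are added. Bleeding within 7 days of the procedure would be affected least, since few deaths can come before it.

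A reader might also infer that mortality here is known to be appreciable, or that the distortion would be worse in older or sicker subgroups. The documents support neither. They give no mortality figure; the composite expected below 14% at 6 months includes stroke, embolism and major bleeding as well as death, and patients with documented life expectancy under 6 months are excluded. SAP 5.3 and Protocol 11.3.3 plan subgroup analyses for the primary endpoints only, which are binary.

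**Conclusion.** The point holds as a minor one. Wherever the Kaplan-Meier sentence is applied to a component other than all-cause death, deaths are censored, the rate is overstated, and the two cause-specific death estimates do not sum to all-cause mortality. The direction is certain. The size rests on assumed mortality and constant hazards: about 1% relative at 2% mortality and 8.3% at 15%, and at most about 0.26 points at 6 months if the composite is held at 14%.

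A reader should not conclude that the safety result is at risk. The additional endpoints carry no hypothesis test, and the primary safety and efficacy tests, their performance goals, sample size and power are untouched. The more practical gap is that the SAP leaves open which of its two estimators supplies each reported rate.

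**What to change.** Amend SAP 5.1 in three respects:

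- Time-to-event rates for every component other than all-cause death use the Aalen-Johansen cumulative incidence function. Death is the competing event for the non-fatal components, and the other cause of death is the competing event for cardiovascular and non-cardiovascular death.
- Kaplan-Meier is kept for all-cause death and for the composite that includes death.
- For each component, the SAP states whether the SAP 7.4 binary rate or the time-to-event estimate is the reported rate.

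The cost is a few lines of SAP text and one programming option, with no change to data collection, sample size or the primary analyses. The downside is a slightly less direct comparison with earlier reports based on Kaplan-Meier; a supplementary Kaplan-Meier estimate, labelled as such, covers that.
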